6.1 Event Reporting Requirements

Adverse events should be reported to Procyrion on the appropriate eCRF using one CRF per AE.

The Investigator must report SAEs and SAEs to Procyrion as soon as possible, but in no circumstances later than 24 working hours after the Investigator first learns of the event, at the following email address:

By email to: [contact]

The initial report must be followed by as much information is available and ideally should include complete documentation, including the time and date of onset, description of the event, severity, duration, actions taken and outcome (if known).

All AEs (regardless of severity or relationship to the study device) will be recorded on the eCRF.

Table 1: Timeline for Reporting of Adverse Events

Type	Report to	Reporting Timeframe (from time of learning of event)
Device Deficiency	Sponsor	Within 2 working days
AE / ADE	Sponsor	Within 2 working days
	EC/IRB	Per EC/IRB reporting requirements
SAE / SADE / USADE / UADE	Sponsor	Within 1 working day
	EC/IRB	Per EC/IRB reporting requirements

6.2 Adverse Event Definitions

Adverse Event (AE): Any untoward medical occurrence, unintended disease or injury, or untoward clinical signs (including abnormal laboratory findings) in participants, users, or other persons, whether or not related to the investigational medical device.

Note: This definition includes events related to the investigational medical device or the comparator. This definition includes events related to the procedures involved. For users or other persons, this definition is restricted to events related to investigational medical devices.

Adverse Device Effect (ADE): Adverse event related to the use of an investigational medical device.

Note: This definition includes adverse events resulting from insufficient or inadequate instructions for use, deployment, implantation, installation, or operation, or any malfunction of the investigational medical device. This definition includes any event resulting from use error or from intentional misuse of the investigational medical device.

Serious Adverse Event (SAE):

A Serious Adverse Event is an adverse event that:

- a. led to death
- b. led to serious deterioration in the health of the participant, that either resulted in:
 - a life-threatening illness or injury, or
 - a permanent impairment of a body structure or a body function, or
 - prolonged hospitalization, or
 - medical or surgical intervention to prevent life-threatening illness or injury or permanent impairment to a body structure of a body function

Note: Planned hospitalization for a pre-existing condition, or a procedure required by the Clinical Investigation Plan, without serious deterioration in health, is not considered a serious adverse event.

Serious Adverse Device Effect (SADE): An adverse device effect that has resulted in any of the consequences characteristic of a serious adverse event.

Device Deficiency: Inadequacy of a medical device with respect to its identity, quality, durability, reliability, safety, or performance.

Note: Device deficiencies include malfunctions, user errors, and inadequate labeling. They can be, but do not have to be, associated with an ADE or AE. Device deficiencies also include effects of electromagnetic interference (EMI). EMI effects can be intermittent; EMI related device effects, degradations, or malfunctions should be reported.

Unanticipated Serious Adverse Device Effect (USADE) / Unanticipated Adverse Device Effect (UADE): Serious adverse device effect which by its nature, incidence, severity or outcome has not been identified in the current version of the risk analysis report (or protocol or instructions for use)

Note: Anticipated Serious Adverse Device Effect (ASADE) is an effect which by its nature, incidence, severity, or outcome has been identified in the risk analysis report.

AEs or SAEs will also be classified as to their relationship to the Investigational Medical Device or procedure, as follows:

Not Related: The event is due to an underlying or concurrent illness or effect of another device, drug or intervention and is not related to the investigational device or procedure.

Related: The event could be attributed to the use of the investigational device or procedure.

Note: The Clinical Event Committee may further categorize relatedness categories such as likely related and definitely related for better understanding of AEs.

If an AE or SAE is determined to be related to the investigational device or procedure, the expectedness of the event would further be classified as anticipated or unanticipated. Expectedness is based on the current literature and experience documented in the risk analysis report and/or contained in the *Investigational Plan, Investigator's Brochure, Report of Prior Investigations, or Instructions for Use*.

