1.1 Background

In partnership with clinical experts, Procyron, Inc. (Procyron) has developed a partial Mechanical Circulatory Support (MCS) system to treat patients with Acute Decompensated Heart Failure (ADHF).

Heart failure (HF) is common, affecting more than 6 million adults and resulting in over 1 million annual hospitalizations in the United States alone.¹ HF is a chronic, progressive condition, marked by episodes of acute decompensation typically requiring hospitalization for stabilization and improvement in symptoms. Unfortunately, outcomes after a hospitalization for decompensated heart failure are poor. The 1-year mortality rate after a heart failure hospitalization has remained high at 20-30%,² and there is additive risk with each subsequent hospitalization.^{3,4}

For patients with chronic, stable HF there are multiple pharmacologic and device-based treatment options.^{1,5-7} However, for patients with ADHF, many medical therapies have been tested in this patient population without success⁸⁻¹⁰ and, as a result, acute HF care remains largely homogenous and unchanged over the past 40 years.^{11,12} The majority of acute HF patients are treated with intravenous loop diuretics with consideration of vasodilator therapies.¹³ High-risk patients with decompensated HF failing conventional therapies are rarely (<2%^{14,15}) considered for temporary or permanent MCS due to a lack of evidence in this population, risk, and cost.¹¹ Positive inotropes are similarly uncommon, used in only 6-12% of these patients due to evidence showing worsened outcomes and higher mortality.^{16,17} Despite optimal medical therapy, 33% of ADHF patients are discharged with persistent congestion.¹⁸

Some degree of renal dysfunction occurs in 91% of ADHF admissions, with 64% of patients having at least moderate (Stage III) dysfunction.¹⁶ These patients represent a particularly high-risk population with poor outcomes. Data from the ADHERE registry of over 110,000 ADHF admissions showed that in-hospital mortality increased from 1.9% for patients with normal renal function to 7.6% in patients with severe dysfunction.¹⁶ In these patients, outcomes are poor due to persistent congestion (90% have persistent congestion after 3 days of pharmacologic therapy¹⁹), increased dose of diuretics,²⁰ and decreased diuretic efficiency.²¹

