3.3 Study Endpoints

3.3.1 Primary Safety Endpoints

- 1 Rate of Occurrence of Serious Adverse Events (rate will be calculated and reported) [timeframe: enrollment to 30 day visit]
- 2 Rate of Occurrence of Serious Procedure Related Adverse Events (rate will be calculated and reported) [timeframe: procedure to 30 day visit]

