Appendix A: Schedule of Visits and Procedures

Category	Pre-Therapy		Aortix Therapy								Post-Therapy			
	Pre-Implant Period (Baseline Monitoring)	Day of Implant (Pre-implant)	Implant to Pump Retrieval					Once Congestion Target is Met and Within 12 hours of Beginning Weaning ^α	Day of Pump Retrieval (Pre-Pump Retrieval)	Cath-Lab Pre-Pump Retrieval	Post-Pump Retrieval Monitoring		Follow-Up: 30 days (± 7 days) from Pump retrieval	
	Current hospitalization once	once	Once (after pump deployed)	2 hours post implant ⊕ (± 30 min)	6 hours post implant (± 30 min) and Every 6 hours (± 1 hour) for 24 hours post implant	Every 24 h (± 2 hours)◆	Pump Speed Changes #	once	once	once	Every 24 h (± 2 hours)	Once at 72 hours post retrieval (± 4 hours) or discharge (whichever is earlier)	once	
Informed Consent ¹	X													
Med History	X													
NYHA Class	X											X	X	
Cardiovascular exam (edema, pulm auscultation, weight)	X	X				X		X				X	X	
Vital Signs: HR, BP, RR #	X	X		X	X	X	X	X		X		X	X	
Height	X													
Fluid Ins and Outs*		X*		X	X	X	X	X		X	X ^β			
Dyspnea Evaluation		X				X		X				X	X	
KCCQ, EQ5D	X												X	
HEMODYNAMICS														
CVP, PAP #		X		X	X	X	X	X		X				
PCWP #		X		X		X	X	X		X				
SvO ₂ , SaO ₂ **		X		X	X	X		X		X				
IMAGING														
Anatomy Screening	X													
Echo	X							X						
Fluoro Image			X							X				
MEDICATIONS	X		Record all cardiovascular/renal medications and medication changes.****										X	
OTHER EVENTS***			Record all adverse events, readmissions and mortality.											

1 Patient must sign informed consent before undergoing PA catheter placement for verification of inclusion criteria for objective measure of congestion or before undergoing imaging to assess anatomy for exclusion criteria for contraindicated anatomy.

α One time assessments to be taken once congestion targets are met or therapy has been deemed ineffective (decision has been made to retrieve device). These assessments should be performed before the pump speed is turned down; within 12 hours of beginning weaning.

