7.8 Main Study Endpoints

7.8.1 Primary Safety

A Primary Safety analysis will be performed for the As-Treated population to include:

- Percentage of patients with Serious Adverse Events (SAE) defined as the total number of patients with a CEC-classified SAE from the time of enrollment through 30 days post-implant Follow-Up, compared to the total number of patients within the population. Patients with two or more CEC-classified SAE will be counted only once.
- Percentage of patients with Serious Procedure Related Adverse Events (SPRAE) defined as the total number of patients with CEC-classified SPRAE from the time of implant procedure through 30 days post-implant Follow-Up, compared to the total number of patients within the population. Patients with two or more CEC-classified SPRAE will be counted only once. Procedure Related Adverse Events will be defined as any AE related to Aortix Pump Deployment Procedure or Aortix Pump Retrieval Procedure.

Descriptive summaries will be provided for both Percentage of patients with SAE and Percentage of patients with SPRAE for As-Treated population. Corresponding listing will be provided for As-Treated Population.

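### The SAE definition lists prolonged hospitalization but not a new or repeat one, so some unplanned readmissions before the 30-day visit are left out of the primary SAE rate as written

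*Protocol*

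**What the plan says.** Protocol section 6.2 makes an event serious if it caused death or "led to serious deterioration in the health of the participant, that either resulted in" one of four outcomes. Two of these are a life-threatening condition and a permanent impairment. The third is "prolonged hospitalization, or" and the fourth is "medical or surgical intervention to prevent life-threatening illness or injury or permanent impairment to a body structure of a body function". A note beneath the list takes out "Planned hospitalization for a pre-existing condition, or a procedure required by the Clinical Investigation Plan, without serious deterioration in health".

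Protocol section 3.3.1 sets the first primary safety endpoint as "Rate of Occurrence of Serious Adverse Events (rate will be calculated and reported) [timeframe: enrollment to 30 day visit". The second is the rate of serious procedure-related events. SAP section 7.8.1 takes as numerator for the first the "total number of patients with a CEC-classified SAE from the time of enrollment through 30 days post-implant Follow-Up", each patient counted once, in the As-Treated population. The second is built the same way but limited to events related to the deployment or retrieval procedure.

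Three other places bear on the question. Appendix A instructs sites to "Record all adverse events, readmissions and mortality". Section 5.2 says that complications may lead either to a further hospital stay or to a longer one, and so treats these as two consequences. Section 1.1 says of decompensated heart failure that "there is additive risk with each subsequent hospitalization".

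**The concern.** Implanted patients are followed for adverse events until 30 days (± 7) after retrieval, and those discharged before then can be readmitted. An unplanned readmission is a new hospitalization. It does not prolong an existing one, so the only hospitalization item in the list does not reach it.

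If the definition is applied as written, the primary SAE rate omits readmissions that meet no other item, in a disease whose course the protocol itself describes through repeated hospitalizations. Serious adverse device effects and their unanticipated subset rest on the same list of consequences, so their classification is affected too. So is the sponsor reporting time in section 6.1, Table 1 (1 working day for SAEs, 2 for other adverse events).

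**Working it through.** The plan states no readmission rate and no expected SAE rate, so there is no figure to reproduce. The check is a reading of the definition, followed by the weight of one patient.

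**Step 1. An unplanned readmission tested against each route in section 6.2.**
- Death: met only if the event was fatal.
- Life-threatening illness or injury: met only if the event reached that level.
- Permanent impairment: met only if impairment resulted.
- Prolonged hospitalization: not met, since the index stay had ended.
- Preventive intervention: met only if treatment was given to avert a life-threatening or permanently impairing outcome. Some access-site infections or late vascular problems would pass. A readmission for recurrent congestion treated with intravenous diuretics could be judged either way.

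A readmission with serious deterioration that meets none of these is not an SAE as written.

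**Step 2. The definition beside the rest of the protocol.**
- Section 5.2 names both a repeat and a prolonged stay. Section 6.2 carries over only the second.
- The note exempts planned admissions. That exemption has little purpose unless unplanned ones can count, but the note does not add a criterion that says so.
- Appendix A records readmissions, so the data exist. The gap is in classification, not in collection.

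**Step 3. Weight per patient.** The target is up to 30 implanted patients (protocol section 7; SAP section 2.3). Each patient whose only qualifying event is a readmission changes the rate by 1/30 = 3.3 percentage points. Adding a criterion can only add patients to the numerator while the denominator stays fixed, so omission can only lower the rate.

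**Step 4. Illustration on assumed rates.** Let s be the proportion of patients with an SAE under the current list and r the proportion with an unplanned readmission. Assume that the two are independent and that no readmission qualifies through another item. The shift is then (1 − s) × r.
- s = 60%, r = 10%: 0.40 × 0.10 = 4 points.
- s = 40%, r = 20%: 0.60 × 0.20 = 12 points, that is 52% instead of 40%.
- s = 20%, r = 30%: 0.80 × 0.30 = 24 points.

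At r = 10%, 30 × 0.10 = 3 readmitted patients are expected, and the chance of at least one is 1 − 0.9^30 = 96%. None of these values of s or r comes from the documents. For given s and r the shift is smaller to the extent that readmissions qualify through another item, or fall in patients who already have an SAE more often than independence implies.

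**The case against.** The strongest reply is that the gap is narrow and already in expert hands. The preventive-intervention item admits many serious readmissions. Section 6.3 sends all clinical events to an independent committee working under a charter, and section 6 allows that committee to change or add to the definitions. Final reports use the committee's classification, so differences between sites do not decide the final rate. The underlying adverse events still appear in the all-event summaries (SAP section 7.9.1). The study is a single-arm feasibility study whose sample size was not statistically derived, and it has no safety threshold.

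Much of this stands, and it limits the point. What it does not do is supply the missing criterion. The committee's power is discretionary, and the charter is not among the documents, so it cannot be assumed to close the gap. Pending events in interim reports carry the investigator's classification (protocol section 6.3), and SAP section 7.13 plans an interim analysis at 15 patients.

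Several stronger readings are tempting but not supported:
- A reader might infer that the protocol contradicts itself. The note points towards counting unplanned admissions, and the list fails to follow through. That is incomplete drafting, not two conflicting rules.
- A reader might infer that all readmissions are excluded. Step 1 shows that several routes remain open.
- A reader might infer that both primary safety rates are affected alike. A congestion readmission judged unrelated to the procedure would not enter the second endpoint under any hospitalization wording.
- A reader might infer that most of the follow-up falls after discharge. No length of stay is given, and section 4.8 provides for patients still in hospital at 30 days.
- A reader might infer that no output will show readmissions. SAP section 7.11 summarizes follow-up information without stating its content, so this cannot be said.

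**Conclusion.** The point holds, at moderate severity. As written, section 6.2 leaves out of the primary SAE rate an unplanned readmission before the 30-day visit that is not fatal, life-threatening or permanently impairing and did not need intervention to prevent a life-threatening or permanently impairing outcome. The serious procedure-related rate is affected only by procedure-related readmissions.

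The direction is certain under a literal reading: omission makes the rate look better. The size is unknown. The firm figure is 3.3 percentage points per affected patient if 30 are implanted. The 4 to 24 points above rest wholly on assumed rates and should not be cited as the bias of this study.

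The severity is not higher because the safety rates are descriptive and no test, margin or success criterion depends on them. It is not trivial either, because the stated rule shapes a primary safety result that is meant to inform later studies.

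**What to change.** In section 6.2 and in the CEC charter, change the item to *new in-patient hospitalization or prolongation of existing hospitalization*. Keep the serious-deterioration condition that governs all four outcomes, and keep the note exempting planned admissions. Have the CEC classify every readmission recorded under Appendix A against the amended definition before either primary safety rate is computed.

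The cost is one line in the protocol and one in the charter, plus classification of readmissions already collected. The downside is a somewhat less favourable SAE rate.

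While SAP section 7.8.1 is open, its 30-day window should be reconciled with the protocol: the SAP describes it as post-implant, whereas protocol section 4.8 times the visit from retrieval. That is a separate matter, but a literal post-implant cut-off would also drop late readmissions.

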6.3 Clinical Event Committee (Safety Committee)

An independent clinical events committee (safety committee) (CEC) will be utilized in this study for adverse event adjudication. All clinical events will be reviewed by the committee. The committee will consist of three physicians who are not participating in the clinical study. The physicians will either be heart failure or interventional specialists. A charter will be developed governing the working of the committee. A chairperson will be designated to run the committee meetings and to work with the committee to ratify the CEC charter prior to any event review. CEC meetings will be scheduled based on the number of events or on trial milestones, but no less than twice a year while the study is ongoing. The last CEC meeting will occur after all subjects have been enrolled and have completed the protocol required follow up period and when all adverse event forms and source documentation have been received by the sponsor.

The sponsor will ensure that adequate source documentation is gathered prior to bring an event before a committee. Additionally, the sponsor will remove all identifiers to site and patient. If an event goes to the CEC and the committee requests additional source documentation, the event will be listed as pending and every attempt will be made to bring the event back to the next meeting.

Reports will show the CEC classification, once final as the final classification. In interim reports, pending events will be listed with the investigator classification. Deaths will be reported separately and the event leading to the death will be shown separately only if designated by the CEC as a separate event. Example, death from cardiac arrest is not reported as both a cardiac arrest and a cardiac arrest death.

7. Statistical Considerations

For the primary purposes of this pilot study, each patient's data will be reviewed individually. Systolic (HF_rEF) and diastolic (HF_pEF) heart failure patients may be analyzed as distinct subgroups. Study results will be summarized using standard statistical analyses (e.g. means and standard deviations compared to baseline, event rates, absolute and relative changes). The sample size of up to thirty (30) implanted patients is based upon industry standards for early stage studies of medical devices; the sample size was not statistically derived. The study will provide data to be used for demonstrating initial device safety and effectiveness in this patient population, as well as providing input for design of future clinical studies of the device. It is estimated that approximately 33% of patients enrolled may not receive the pump due to anatomical requirements or right PA catheterization requirements not being met or inability to implant the pump. Therefore, we plan to enroll up to 60 patients to yield 30 implanted patients. An interim report may be generated prior to completion of enrollment for regulatory or publication purposes. Enrollment at a given site may be restricted to ensure a balanced enrollment across sites and geographies.

8. Ethical, Regulatory, and Administrative Considerations

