3.4 Study Population

This study will enroll up to 60 patients in order to treat 30 patients using Aortix with ADHF (irrespective of ejection fraction) refractory to medical management with persistent clinical signs of congestion and worsening renal function.

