2.3 Determination of Sample Size

The sample size of up to thirty (30) implanted patients is based upon industry standards for early stage studies of medical devices; the sample size was not statistically derived.

The study will provide data to be used for demonstrating initial device safety and effectiveness in this patient population, as well as providing input for design of future clinical studies of the device. It is estimated that approximately 50% of patients enrolled may not receive the pump due to anatomical requirements or right heart PA catheterization requirements not being met or inability to implant the pump. Therefore, we plan to enroll up to 60 patients to yield 30 implanted patients.

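### The protocol's 33% non-implant estimate gives about 45 enrolled for 30 implants, not the 60 it is said to justify; the SAP gives 50% for the same quantity, and only 50% gives 60

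*Protocol*

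**What the plan says.** Protocol section 7 (Statistical Considerations) fixes the treated number by convention: "The sample size of up to thirty (30) implanted patients is based upon industry standards for early stage studies of medical devices", and it adds that "the sample size was not statistically derived". It then turns to enrolment. The expected loss between consent and implant is put at about a third: "It is estimated that approximately 33% of patients enrolled may not receive the pump", with unsuitable anatomy, unmet PA catheterisation requirements and inability to implant as the reasons. The next sentence draws the conclusion: "Therefore, we plan to enroll up to 60 patients to yield 30 implanted patients".

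The protocol summary and section 3.4 repeat the pair of numbers without a rate: "This study will enroll up to 60 patients in order to treat 30 patients using Aortix".

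SAP section 2.3 (Determination of Sample Size) follows the protocol almost word for word, with the same reasons for loss and the same 60 and 30, but with a different rate: "It is estimated that approximately 50% of patients enrolled may not receive the pump due to anatomical requirements".

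The denominator is the same in both. Protocol section 4.2 counts a patient as enrolled at signature of the consent form, before imaging screening starts, and SAP section 6.1.1 defines the All Enrolled population by that signature. SAP section 7.14, which lists changes from the protocol's analyses, names only the urine-output timepoint and does not mention the rate.

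**The concern.** The 60 in protocol section 7 is presented as a result. The text gives a loss rate, then draws the enrolment number from it as a consequence. A reader who repeats the step with the stated 33% does not get 60. A reader who turns to the SAP to resolve this finds another rate for the same quantity.

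At stake is the stated justification for the enrolment ceiling. The summary and section 3.4 only restate 60 and 30, so this sentence is the whole quantitative argument for 60. A reader of the protocol is told to expect that one enrolled patient in three will not receive the pump; a reader of the SAP is told one in two. The two rates also differ on whether 60 is comfortable or only just enough to reach 30. Section 7 says the study is meant to inform the design of later studies, so its planning assumption should be unambiguous.

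**Working it through.** **Inputs**

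- Target implants: 30 (protocol section 7; SAP section 2.3).
- Enrolment ceiling: 60 (protocol summary, sections 3.4 and 7; SAP section 2.3).
- Loss rate d: 0.33 (protocol section 7) or 0.50 (SAP section 2.3).

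**Step 1: try to reproduce the plan's 60.** The number to enrol is N = 30/(1 − d).

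- d = 0.33: 30/0.67 = 44.8, so 45.
- d = 1/3: 30/(2/3) = 45.
- d = 0.50: 30/0.50 = 60.

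The common shortcut of inflating by (1 + d) does not rescue the protocol's figure: 30 × 1.33 = 39.9, about 40, which is further from 60.

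**Step 2: work backwards.**

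- Loss rate implied by 60 and 30: 1 − 30/60 = 0.50.
- Expected implants from 60 at d = 0.33: 60 × 0.67 = 40.2.
- Expected implants from 60 at d = 0.50: 60 × 0.50 = 30.

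The protocol's rate therefore misses its own enrolment figure by 60 − 45 = 15 patients. The SAP's rate fits exactly.

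**Step 3: could 60 be a cap with a margin?** Treat each enrolled patient as implanted independently with probability 1 − d, and compute the binomial probability of at least 30 implants from N enrolled.

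| N enrolled | d = 0.33 | d = 0.50 |
|---|---|---|
| 45 | 0.588 | 0.018 |
| 50 | 0.884 | 0.101 |
| 54 | 0.971 | 0.248 |
| 60 | 0.998 | 0.551 |

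At d = 0.33, the smallest N that reaches 30 with probability at least 0.95 is 53, and for 0.99 it is 57. So 60 would be a very generous cap under the protocol's rate. Under the SAP's rate it has no margin: 60 delivers 30 on average and falls short with probability 1 − 0.551 = 0.449.

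**Step 4: rates in between.** With N = 60, the probability of at least 30 implants is 0.991 at d = 0.36, 0.956 at d = 0.40 and 0.818 at d = 0.45. The assurance that 60 provides falls quickly over the range between the two documents' estimates, so the choice of rate matters to what the ceiling means.

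**The case against.** **The 60 is a ceiling.** Both documents say up to 60, and the 30 is also stated as an upper figure. A ceiling above an expected 45 is a workable plan, and at a 33% loss it almost guarantees 30 implants. This stands in part: the calculation does not show that 60 is a bad number. It does not rescue the sentence, because no margin is stated and the text draws 60 from the 33% as the number that yields 30. A margin also would not explain why the SAP gives 50% for the same quantity.

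**It may be a difference between revisions.** The SAP says it was written from protocol Rev G, and the revision letter of the protocol is not visible in the text available for review. A mismatch cannot be excluded as the source of the difference between the documents. It would not repair the arithmetic within section 7.

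**The sample size was not statistically derived.** True of the 30, and it limits the consequence. The 60 is a separate figure for which a derivation is given.

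Three stronger readings are tempting, and the documents do not support them.

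- A reader might infer that feasibility will be judged against this rate. No endpoint in protocol section 3.3 or SAP section 5 uses screen failure or enrolment yield, and SAP section 7.1 only counts screen failures. Deployment success (SAP section 7.8.2) has attempted implants as its denominator, so patients screened out earlier do not enter it.
- A reader might infer that the rate fixes how many patients are screened without receiving a pump. The true loss rate, the target of 30 and the cap determine that. If the true loss is 33%, 30 implants are expected after about 45 enrolments whatever the cap. Nor does every enrolled patient need new procedures: section 4.2 calls for PA catheter placement only if not already done, and a protocol footnote allows imaging from the previous 12 months to be reused.
- A reader might infer that 50% must be the correct rate because it reproduces 60. Neither document gives a basis for either rate. Choosing 50% on that ground would be fitting the assumption to the answer.

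**Conclusion.** The point holds as an error in the justification of the enrolment number. Protocol section 7 does not support its own 60: the stated rate gives about 45, a gap of 15 patients, or about 40 implants instead of 30 if all 60 are enrolled. The protocol and SAP give different rates, 33% and 50%, for one quantity with one denominator, and only the SAP's is consistent with 60 and 30.

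The consequence is limited. The treated number stays at 30, and no power, error rate, analysis population or endpoint analysis changes. Which rate the sponsor believes cannot be settled from the documents.

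The enrolment arithmetic needs no assumption beyond the stated figures. The probabilities 0.998 and 0.55 assume independent patients with a common implant probability. Real variation between sites, or uncertainty in the rate itself, would alter them.

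**What to change.** State one non-implant estimate, with its basis, in protocol section 7 and SAP section 2.3, and make the enrolment figure follow from it.

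- **If the estimate is 33%:** give about 45 as the expected enrolment, describe 60 as a cap with an explicit margin (probability 0.998 of at least 30 implants under the binomial assumption), and correct the rate in SAP section 2.3.
- **If the estimate is 50%:** correct the rate in protocol section 7, and state that 60 yields 30 only in expectation (probability 0.55 of at least 30), so that fewer than 30 implants is a realistic outcome.

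If the sponsor holds another value, the same formula applies and both documents need the new figure. The cost is a sentence or two in each document. The target of 30 and the analyses are unchanged, and under either option the ceiling of 60 can stay if it is labelled for what it is.
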